## 8.2.1 Partial or Missing Dates

The following conventions will be used to impute missing portions of dates for AEs and concomitant medications. Note that the imputed values outlined here may not always provide the most conservative date. In those circumstances, the imputed value may be replaced by a date that will lead to a more conservative analysis.

Start Dates:

- 1. If the year is unknown, then the date will not be imputed and will be assigned a missing value.
- 2. If the month is unknown, then:
  - a. The month and day of the first dose date will be imputed if the year matches the first dose date year.
  - b. Otherwise, 'January' will be assigned.
- 3. If the day is unknown, then:
  - a. The day of the first dose date will be imputed if the month and year match the first dose date month and year.
  - b. Otherwise, the first day of the month will be assigned.

Stop Dates:

- 1. If the year is unknown, then the date will not be imputed and will be assigned a missing value.
- 2. If the month is unknown, then 'December' will be assigned.
- 3. If the day is unknown, then the last day of the month will be assigned.

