3.3 Safety Objectives

The overall safety objective is to assess severity, incidence and frequency of AEs, AEs of Special Interest (AESIs), and Serious Adverse Events (SAEs), concomitant medication use, suicidal ideation and behavior, and vital signs to support the package insert for MDMA-assisted psychotherapy. The following safety objectives will evaluate the safety of MDMA-assisted psychotherapy.

- 1. Assess incidence of AEs during Experimental Sessions that may be indicative of a medical complication of the Investigational Product (IP), such as clinical signs and symptoms of chest pain, shortness of breath, or neurological symptoms or any other signs or symptoms that prompt additional vital sign measurements
- 2. Assess incidence of AEs by severity
- 3. Assess incidence of Treatment Emergent AEs (TEAEs) by severity
- 4. Assess incidence of TEAEs by severity taken during an Experimental Session and 2 days after IP administration
- 5. Assess incidence of AESIs, defined as AEs specified in the protocol related to cardiac function and abuse liability
- 6. Assess incidence of AEs by severity categorized as leading to discontinuation of IP, resulting in death or hospitalization, and continuing at Study Termination
- 7. Assess incidence of SAEs
- 8. Assess incidence of psychiatric concomitant medications taken during an Experimental Session and 2 days after IP administration
- 9. Assess incidence of any psychiatric concomitant medications taken during the Treatment Period

- MP16 Protocol Amendment 1 Version 1: 03 January 2018
- 10. Assess incidence of serious suicidal ideation and positive suicidal behavior assessed with the Columbia Suicide Severity Rating Scale (C-SSRS)
- 11. Assess mean changes in blood pressure, heart rate, and body temperature from pre-IP administration to end of each Experimental Session

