## 8.8.3 Concomitant Medications

A secondary measure of safety will be the reporting of concomitant medications. All concomitant medications collected from Screening to Study Termination will be categorized as follows:

- Pretreatment medications are defined as medications taken prior to and after signing informed consent and those taken during the Preparatory Period prior to the first Experimental Session. A stop date is expected prior to the first Experimental Session for any medications requiring a change in dose, a skipped dose, or tapering.
- Treatment Period concomitant medications are defined as those taken or continued during the Treatment Period from the first Experimental Session to the last Integrative Session. A stop date is expected prior to the each Experimental Session for any medications requiring a change in dose, a skipped dose, or tapering.
- Concomitant medications with a start date of the day of and two days after IP administration
- Follow-up Period concomitant medications are defined as those taken or continued during the Follow-up Period after the last Integrative Session through Termination
- Any concomitant medications that are tapered
- Any concomitant medications that are taken to treat an AE
- Any concomitant medications that are taken to treat an SAE
- Any excluded concomitant medications taken as a deviation from the protocol.

Concomitant medications on case report forms will be classified using the WHO Drug Dictionary EnhancedTM (WHO DDE). Frequency and incidence of concomitant medications will be displayed by generic name, sorted by class, and summarized by treatment group, analysis set, and category as defined above. Concomitant medications will be analyzed and presented as follows:

- Concomitant medications taken on the day of and two days after IP administration will be presented separately
- Any psychiatric concomitant medications by period.

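### SAP 8.2.1 dates a partially dated concomitant medication to Session 1 without checking its stop date or whether it was already recorded before dosing

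*SAP*

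**What the plan says.** SAP 8.2.1 opens with its scope: "The following conventions will be used to impute missing portions of dates for AEs and concomitant medications". The rules for start dates are:

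- Month unknown (rule 2a): "The month and day of the first dose date will be imputed if the year matches the first dose date year". For any other year (rule 2b): "Otherwise, 'January' will be assigned".
- Day unknown (rule 3a): "The day of the first dose date will be imputed if the month and year match the first dose date month and year". In any other month, the first of the month is used.

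For stop dates: "If the month is unknown, then 'December' will be assigned", and "If the day is unknown, then the last day of the month will be assigned".

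The section adds that these values may not always be the most conservative and that a more conservative date may be substituted. It does not say when, or what conservative means for a medication.

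SAP 8.8.3 then defines a category by start date: "Concomitant medications with a start date of the day of and two days after IP administration". It also expects medications that are tapered to have a stop date before the first Experimental Session. Protocol 12.1 sets the gap at no less than five half-lives plus one week, and has all medications recorded from Screening onward.

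**The concern.** Defaulting an uncertain start to the first dose is a familiar convention for adverse events, where it makes a doubtful event treatment-emergent. Medications are different. Many are recorded because they were already in use before dosing, and the trial requires psychiatric drugs to be stopped before Session 1. For such a record the team already knows that the start lies before first dose, and often knows the stop date too. The rule ignores both facts.

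Two errors follow. A drug begun earlier in the dosing year is reported as newly started on the day of Session 1. A drug that was tapered as planned acquires a start date later than its stop date, which is impossible. Dosing-day medication use is something the trial wants to describe, so false entries in a listing built on that window are worth preventing.

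**Working it through.** The documents give no figure to reproduce, so the check applies the rules literally.

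**Inputs.** The start and stop rules are from SAP 8.2.1, the start-date category from SAP 8.8.3, and the minimum taper gap from Protocol 12.1. Assumed for illustration: first dose on 15 June 2018, half-lives of 0.5 to 6 days, and a start known only to the year.

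**Step 1: start date.**

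- Start year 2018, month unknown: rule 2a gives 15 June 2018. This is day 0, so the drug enters the start-date category.
- Start year 2017, month unknown: January 2017. No error of this kind.

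**Step 2: start against stop for a tapered drug.** Latest compliant stop = first dose − (5 × half-life + 7 days), in whole days.

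| Half-life (days) | Minimum gap (days) | Latest stop | Imputed start | Start after stop by |
|---|---|---|---|---|
| 0.5 | 9.5, taken as 10 | 5 June | 15 June | 10 days |
| 1 | 12 | 3 June | 15 June | 12 days |
| 2 | 17 | 29 May | 15 June | 17 days |
| 6 | 37 | 9 May | 15 June | 37 days |

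Because the gap is 5 × half-life + 7, the reversal always exceeds 7 days.

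**Step 3: rule 3a.** Start in June with the day unknown, stop on 5 June: the imputed start is 15 June, 10 days after the stop.

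**Step 4: all dates in one year.** Take every first-dose day in 2018 and every earlier same-year true start, with the start month unknown and the stop 8 days before first dose. The number of cases is 1 + 2 + … + 356 = 356 × 357 / 2 = 63,546. All 63,546 land on the dosing day and all 63,546 start after they stop. This follows by construction, because rule 2a never uses the stop date.

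**Step 5: limits on reach.**

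- If start dates were uniform over the 365 days before dosing (an assumption), the share falling in the first-dose year is 14/365 = 4% for a dose on 15 January, 165/365 = 45% on 15 June and 348/365 = 95% on 15 December.
- If the stop month is unknown too, the stop becomes 31 December 2018. There is then no reversal, but the tapered drug appears to run through dosing.
- Rule 3a reaches fewer drugs. Under Protocol 8.1.3 and 8.2.1, Visit 1 may share a day with Visit 0, Visit 2 is at least 2 days after Visit 1, and Session 1 is at least 2 weeks after Visit 2. Enrollment is therefore at least 2 + 14 = 16 days before Session 1. A drug ongoing at Enrollment can share the dosing month only if the dose falls on the 17th or later.

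**Step 6: the remedies.** Capping the start at the known stop leaves 0 of 63,546 reversals and 0 of 63,546 false entries in the dosing window. Using 1 January of the known year gives the same 0 and 0. The cap does nothing for an ongoing drug, which has no stop date, so a second rule is needed. For a drug ongoing at Enrollment, the earliest possible date (1 January, or the first of the known month) lies on or before Enrollment. By the 16-day minimum it cannot fall in the dosing window.

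**The case against.** The strongest reply is that the consequences are small and that several larger ones do not follow.

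- **The stated safety objective.** A reader might infer that it is biased. Protocol 3.3 says "Assess incidence of psychiatric concomitant medications taken during an Experimental Session and 2 days after IP administration", which concerns drugs taken, not drugs started. A drug still in use on the dosing day belongs in that count whatever its imputed start, and a tapered drug with a known stop is excluded by a test that uses the stop. Only the SAP 8.8.3 start-date category is clearly affected.
- **Adverse events.** A reader might infer that an event from Session 2 or 3 would be moved to Session 1 and distort the tables. The tables planned in Protocol 14.1.2 and SAP 8.8.2 pool dosing days and are not split by session number, so such an event stays in the same table. The first-dose default is also the cautious choice when onset is uncertain, and events are collected prospectively at visits and in four calls in the week after each dose.
- **A fixed inflation.** A reader might take each mis-dated drug to add 1/60 = 1.7 percentage points. That holds only for a participant not already counted in that row, and only if the denominator is 60, which is an enrollment ceiling.
- **Frequency.** Medical records are required at Screening and the site physician confirms medications, so few dates may be partial. Drugs begun in earlier years go to January.
- **The override.** It might be used to repair individual records.

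All but the last stand as limits on size. The override is optional and has no trigger. Counting more dosing-day medication could itself be called conservative, so it cannot be relied on. It would be equally unsupported to say that it could never correct a record.

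**Conclusion.** The rule is wrong as written for medications, with minor impact. Where the start year matches first dose and the month is missing, or the start month and year match and the day is missing, SAP 8.2.1 dates the drug to Session 1 even against a record showing earlier use. That puts it falsely in the start-date category. For a tapered drug with a known stop, it gives a start after the stop, by 10 to 37 days in the worked case.

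This rests on a literal reading of the rules and on the override not being applied. The dates and half-lives are illustrative. The direction of the error depends on none of them, but its frequency depends on the number of partial dates, which the documents do not give. The effect stops at descriptive medication tables that use start dates.

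**What to change.** Amend SAP 8.2.1 in two places.

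1. State that an imputed start date may not be later than a known stop date, for adverse events as well as medications.
2. For medications recorded at Screening or ongoing at Enrollment, impute the earliest date consistent with the known parts: 1 January of the known year, or the first day of the known month. Keep the first-dose default for medications only when no record places the start before first dose.

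Apart from the stop-date check, leave the first-dose default for adverse events unchanged. Both rules use data already collected. The cost is a short SAP edit and a small amount of extra programming.

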14.1.2 Safety Analyses

Safety data will be summarized by exposure to IP, unsolicited AEs, concomitant medications, suicidal ideation and behavior, and vital signs overall. If a participant has more than one AE mapped to the same PT, that AE will be reported once using the highest severity. AEs that occur on Day 0 (Experimental Session), Day 1, Day 2 after IP administration will be presented separately. Report incidence of AEs during Experimental Sessions such as clinical signs and symptoms, such as chest pain, shortness of breath, or neurological symptoms or any other signs or symptoms that may be indicative of a medical complication of the IP.

Frequency and incidence of concomitant medications will be displayed by generic name, sorted by class, and summarized by analysis set and category. Concomitant medications taken on Day 0 (Experimental Session), Day 1, Day 2 after IP administration will be presented separately. Any psychiatric concomitant medications will be tabulated by period (Preparatory, Treatment Period, Follow-up Period). Frequency and incidence of positive or serious ideation and suicidal behavior will be presented using descriptive statistics of C-SSRS scores in tabular format. Vital signs (heart rate, blood pressure, and body temperature) for Experimental Sessions will be summarized using descriptive statistics in tabular format listing values at pre-IP administration, prior to the supplemental dose, and at the end of each Experimental Session. Additional details are available in the Statistical Analysis Plan.

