## 8.8.2 Analysis of Adverse Events

The primary measure of safety will be the reporting of unsolicited AEs. All AEs collected from Enrollment to Termination will be categorized as follows:

- Pretreatment AEs are defined as AEs that occur during the Preparatory Period prior to the first dose in the first Experimental Session
- Treatment Emergent AEs are defined as AEs that occur during the Treatment Period from the first Experimental Session to the last Integrative Session
- AEs that occur on and two days after MDMA or placebo administration
- AESIs are defined as AEs specified in the protocol related to cardiac function and abuse liability
- Follow-up Period AEs are defined as AEs that occur during the Follow-up Period after the last Integrative Session through Termination
- AEs leading to discontinuation of IP
- AEs resulting in death or hospitalization.
- SAEs
- AEs continuing at Termination.

Verbatim terms on case report forms will be mapped to preferred terms (PT) and system organ class (SOC) using the Medical Dictionary for Regulatory Activities (MedDRA) Version 17.0. Frequency and incidence of AEs will be displayed by PT, sorted by SOC, and summarized by treatment group, analysis set, category (as defined above), severity, and seriousness. AEs will be analyzed and presented as follows:

- If a participant has more than one AE mapped to the same PT, that AE will be reported once using the highest severity
- Relationship will be determined based on relative incidence of TEAEs with at least twofold difference between MDMA vs. placebo
- Compare relative incidence of AEs during Experimental Sessions such as clinical signs and symptoms, such as chest pain, shortness of breath, or neurological symptoms or any other signs or symptoms that may be indicative of a medical complication of the investigational product
- AEs that occur on day of Experimental Sessions and two days after IP administration will be presented separately.

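### The rule for AEs with an unknown start day is anchored to the first dose only, so most such events after Sessions 2 and 3 drop out of the Day 0-2 table by default

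*SAP*

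**What the plan says.** SAP 8.2.1 sets the date conventions: "The following conventions will be used to impute missing portions of dates for AEs and concomitant medications". When only the start day is unknown, rule 3a reads: "The day of the first dose date will be imputed if the month and year match the first dose date month and year". Rule 3b covers every other month: "Otherwise, the first day of the month will be assigned". Neither rule refers to the second or third Experimental Session.

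The section then qualifies itself: "Note that the imputed values outlined here may not always provide the most conservative date". It adds: "In those circumstances, the imputed value may be replaced by a date that will lead to a more conservative analysis".

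The dates feed a separate presentation of acute events. SAP 8.8.2 states: "AEs that occur on day of Experimental Sessions and two days after IP administration will be presented separately". Protocol 14.1.2 states: "AEs that occur on Day 0 (Experimental Session), Day 1, Day 2 after IP administration will be presented separately". This window serves a listed safety objective (item 4 in Protocol 3.3, repeated in SAP 3.3). Protocol 8.3 places the three Experimental Sessions 3 to 5 weeks apart.

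**The concern.** A first-dose anchor suits a trial with one start of treatment. Here there are three dosing days, and the acute window opens again at each of them. Rule 3a protects Session 1: an undated event in that month is placed on the dosing day and counted as acute. Sessions 2 and 3 have no such protection. An undated event in one of their months usually goes to the 1st, before the session it followed.

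What is at stake is the completeness of the Day 0-2 AE presentation. By default it keeps partially dated acute events from Session 1 and loses most of those from Sessions 2 and 3. The loss is in the direction of fewer reported acute events, which is the opposite of what a safety imputation rule is normally meant to do.

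**Working it through.** The plan gives no figure on this point, so there is none to reproduce. The check applies rules 3a and 3b literally.

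**Inputs**
- Imputation rules 3a and 3b: SAP 8.2.1.
- Window: the session day and the two days after it (SAP 8.8.2, Protocol 14.1.2).
- Gap between sessions: 3 to 5 weeks, i.e. 21 to 35 days (Protocol 8.3).
- Assumptions: Session 1 is equally likely on each day of a 365-day year, and every gap from 21 to 35 days is equally likely. Fixed gaps of 21, 28 and 35 days were also run.
- Event: true onset on Day 0, 1 or 2, with month and year known and day unknown.

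**Share that stays in its own window (Sessions 2 and 3).** An event placed on the 1st stays only if that date is on or after its session. Per calendar month:
- session on the 1st: 3 onset days stay;
- session on the last day: 2 stay (Days 1 and 2 fall in the next month);
- session on the second-last day: 1 stays (Day 2).

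That is 6 per month, so 6 × 12 = 72 of 365 × 3 = 1,095 session-onset combinations, or 6.6%. The other 93.4% are imputed to before their own session. Rule 3a does not change this split, because it also moves the date back, to Session 1.

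**Share that leaves every window.** Some of the 93.4% land in an earlier session's window and so remain in a pooled Day 0-2 table. Full enumeration gives:

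| Gap | Session | Own window | Earlier session's window | Outside every window |
|---|---|---|---|---|
| 21-35 days, uniform | 2 | 6.6% | 13.2% | 80.2% |
| 21-35 days, uniform | 3 | 6.6% | 6.2% | 87.2% |
| 21 days | 2 | 6.6% | 34.2% | 59.2% |
| 21 days | 3 | 6.6% | 9.9% | 83.6% |
| 28 days | 2 | 6.6% | 11.2% | 82.2% |
| 28 days | 3 | 6.6% | 8.9% | 84.5% |
| 35 days | 2 or 3 | 6.6% | 0.0% | 93.4% |

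Rows may miss 100% by 0.1 through rounding. Of the 13.2% for Session 2, 8.8 points arise under rule 3a. The other 4.4 points (13.2 − 8.8) are events placed on a 1st of the month that lies in Session 1's window. Session 1 events stay in their window in 100% of cases.

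**Treatment-emergent status.** An event in the first-dose month goes to the first-dose date, and an event in a later month goes to a 1st after that date. No Session 2 or 3 event is placed before the first dose (0%).

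**Examples**
- Session 1 on 5 March, Session 2 on 9 April (35 days), event on 10 April. The imputed date is 1 April, 8 days before Session 2 and outside every window.
- Session 1 on 5 March, Session 2 on 27 March (22 days), event on 28 March. The imputed date is 5 March. The event stays in a pooled table, under the Session 1 date.

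**The case against.** The strongest objection is that the triggering case should be rare. AEs are recorded at the end of the session (Protocol 8.3.1), at the Integrative Session the next morning (8.3.3) and by telephone on the second day (8.3.2). A Day 0-2 event with a known month and no day needs a late or incomplete report. The documents give no rate of partial dates, so the number affected cannot be computed. In up to 60 participants it may be close to zero. This stands, and it limits the importance of the point.

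The SAP also admits that its defaults may not be conservative and allows a substitute date. This stands only in part. The permission is optional and has no trigger, no decision-maker and no replacement date, so two programmers could build different tables. SAP 9.0 also provides for preliminary analyses throughout this open-label study, so the choice could be made with data in view.

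Third, any session anchor will pull in some AEs that began later, after the close contacts have ended. That is true. Rule 3a already does this for Session 1: under the assumptions above, it contributes to 68.8% of undated events from Days 3-20 after Session 1 landing in a Day 0-2 window, against 11.6% and 11.0% after Sessions 2 and 3.

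Three stronger readings are tempting but not supported:
- **Acute events at 120 mg are credited to the 80 mg session.** SAP 8.8.2 lists treatment group, analysis set, category, severity and seriousness as AE breakdowns, not session or dose. Protocol 14.1.2 summarises safety overall, and the by-initial-dose summaries in Protocol 14.1 concern outcome measures. An event moved to the Session 1 date stays in the specified table.
- **93% of these events are lost.** That is the share placed before their own session, not the share outside every window.
- **Events cease to be treatment-emergent.** None does.

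**Conclusion.** The point holds in a limited form. The start-date rule has one dosing anchor in a trial with three dosing days. Its default removes about 80% of day-missing Day 0-2 events after Session 2, and about 87% after Session 3, from every Day 0-2 window, while all such Session 1 events stay. These shares assume uniform start dates and gaps. Over fixed gaps of 21 to 35 days they run from 59.2% to 93.4% for Session 2 and from 83.6% to 93.4% for Session 3. They are conditional on the day being missing and on the optional override not being used.

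The effect on AE reporting is confined to the Day 0-2 presentation, and the count involved should be small. It still merits correction, because the rule misplaces events in a table that answers a stated safety objective, and the safeguard as written is not reproducible.

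**What to change.** In SAP 8.2.1, replace start-date rule 3b for AEs with wording such as:

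*If the day is unknown and the known month and year contain one or more Experimental Sessions, impute the date of the latest session in that month that is not after the known stop date or the contact at which the AE was first recorded. Otherwise impute the first day of the month.*

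Apply the same logic in rule 3a when two sessions share a month. State in the Day 0-2 AE table how many of its events have imputed dates. In the first example above, the event of 10 April would then be placed on 9 April and counted.

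The same conventions also feed the medication category defined as "Concomitant medications with a start date of the day of and two days after IP administration", so the SAP should say whether the session anchor applies there too.

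The cost is one paragraph of SAP text and a small programming change, with no new data collection. The downside is that some later-onset AEs without a day will be counted in the Day 0-2 table, so its counts may look slightly less favourable. That is in keeping with the conservative aim the SAP already states, and the reported number of imputed dates lets a reader judge it.
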